7.0 Data and Specimen Storage for Future Research

- 7.1 No data or specimens will be banked for future use.
- 7.2 N/A
- 7.3 N/A

8.0 Sharing of Results with Subjects

8.1 Study results will be shared with subjects and subject's primary care physicians upon request. Shared data will be encrypted and will remain behind the VA firewall.

9.0 Study Timelines

- 9.1 It should take up to 2-4 weeks to fit Brasthesis (one to three prosthetic clinic visits). The Brasthesis wearing period is 4-weeks. Data collection could add a week before and a week after the wearing period depending on scheduling.
- 9.2 The entire project will take one to two years including dissemination of findings.

10.0 Inclusion and Exclusion Criteria

- 10.1 Potential subject will self-identify with the project manager whether they meet the inclusion criteria. Inclusion and exclusion criteria are observable.
- 10.2 The inclusion criteria are: (1) mid to short transhumeral, shoulder, or interscapularthoracic unilateral amputation, (2) have an existing myoelectric, hybrid, body-powered or cosmetic prosthetic limb that they use or have abandoned. The additional resources to train a participant with no prosthetic experience is beyond the scope of this study.
- 10.3 The exclusion criteria: (1) open wounds in the upper torso or extremities, (2) women who do not have an existing prosthesis would exceed the time resources for a SPIRE funding mechanism.

- 10.4 A subject will be ineligible to continue participation if they develop a condition on their residual body part that disallows them to wear a prosthesis, such as a bone spur or open sore.
- 10.5 No students, employees, socially and/or economically disadvantaged, or wards of the state will be included.

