4.0 Safety Endpoints

4.1 Primary endpoints are satisfaction, function, and comfort.

The secondary endpoints are the interface pressure that drives comfort and range of motion that drive functional movement.

Page 7 of 18 Revised: July 6, 2023

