 and problems that may have occurred during the week.
- During this baseline phone meeting, the two sub-surveys of the Orthotic and Prosthetic User Survey (OPUS) and the one-item Socket Comfort Scale will be administered. The socket comfort scale is a one-item analog 0-10 self report rating scale. There is no published pdf for this one-item scale. The score is included in the Data Collection Sheet Item #12.
- The project manager will extract demographic and clinical information from the medical record.

- The participant will be scheduled for a fitting at a prosthetic clinic, either at the JAHVH study site or their home VA prosthetic clinic, the clinic regularly attend in/ near their place of residence. The fitting process will begin with introductions. The participant will don the prosthesis/traditional harness. We measure functional range of motion (shoulder flexion/extension and abduction/adduction) with a goniometer while participants are wearing their conventional prosthetic harness.
- Also at the fitting visit, we will use the Tekscan Artec Studio system to quantify pressure between the prosthetic socket and residual limb and around the contralateral axilla while wearing the traditional harness. Pressure mapping entails attaching a paper thin, flexible sensor, trimmed to match anatomical contours with double sided adhesive tape directly to the skin to securely cover each participant's residual limb and in the contralateral axilla region then mapping pressure at three positions: (1) prepressure will be measured wearing the prosthetic liner with the residual limb positioned neutral at their side, (2) wearing prosthesis with 90 degrees prosthetic elbow flexion, and (3) full elbow extension with shoulder flexion in the plane of the scapula [5].

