- The subject will then don the Shefit® bra over the traditional harness. We will mark where the traditional harness and Shefit® overlap. D-rings from the spare bra will be riveted at the marked spots (for our prototype, the patient required two d-rings anterior and posterior). Once the d-rings have been riveted to the prosthesis, the participant will don modified Shefit bra/Brasthesis. At this point the custom fitting will begin which will vary from participant to participant. Our prototype patient had gaping at the top of the socket that was successfully addressed by adding a strap from the spare bra cross the participant's back. The participant guided the prosthetist as to where she needed support. The prosthetist riveted a third central d-ring to accommodate a diagonal backstrap. This individualization may vary for each of the five subjects and is the primary purpose for this proof of concept study.
- We will replace the front zipper with a commercially available magnetic bra closure for one-handed donning, if desired
- Participants will be provided a Jawbone UP 24 or OPOS1 activity tracker by the
 prosthetist once the prosthesis has been successfully fit using Brasthesis. Jawbone
 API software or OPOS1 software provides direct export of accelerometer that
 contains no PHI or PII (deidentified) data to approximate wear time to the hour of
 each day.
- The prosthetic and research teams will be available should the participant need adjustment to the harness and prosthetic fit, per standard care.
- At the end of the four-week wearing period, the participant will return to the clinic. Range of motion measurement and pressure mapping will be repeated but this time with the Brasthesis rather than the traditional harness.

- The outcome measures administered at baseline will be completed again post-intervention. The project manager will conduct a brief interview for the participant and prosthetic team to understand the experience of being fit with and using Brasthesis. This interview will be audio recorded.
- The participant will be told that after all five participants have completed Brasthesis, a focus group will be held for the purpose of brainstorming how to proceed with the manufacturing and marketing of Brasthesis. This focus group will be audio recorded.

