- 6.3 All procedures will be performed solely for research purposes except for the prosthetic clinic visits for Brasthesis and prosthetic adjustment as needed. Returning to the amputation clinic for Brasthesis/harness or prosthetic adjustment are standard care.
- 6.4 Participants will be under the care of experience amputee and prosthetic clinicians including occupational therapists, physicians, prosthetists, and engineers who will be able to efficiently and empathetically address any challenge that may occur during the Brasthesis fitting process and wearing period.

Participants can return to the use of their traditional harness at any time. They will not be withdrawn from the study if they return to using their traditional harness as data on why participants use or do not use Brasthesis are needed to address research questions.

Participants can contact the project manager, an occupational therapist with extensive upper limb amputation and prosthetic experience, at any time.

- 6.5 Aim one of this project will capture existing data:
 - Data to be collected is displayed in the Table below and the uploaded data capture sheet.

Table 1 Variables			
Variable	RQ	Definition	Source, Timepoint
		Outcomes	
Wearing time	1.1	Days/week, hours/day, Traditional versus Brasthesis™	Weekly communication
		Jawbone Up 24 or OPOS1 activity tracker	Automated
Satisfaction	1.2	OPUS Satisfaction with Device	
Function	1.3	OPUS UE Functional Status [22] (Appendix 5)	Traditional – pre
Comfort	1.4	Socket Comfort Score [23], 0-10 numeric rating scale	Brasthesis - post
Barriers	1.5	Described by participants and clinicians	Post interview (QL)
Pressure	2.1,2.2	Tekscan F-Socket (Appendix 7)	Prosthetist, engineer, post
Demographic and Clinical Variables			
Age		Age on date of baseline data collection	
Sex		Male, female, other	
Race/ethnicity	All	Caucasian, African American, Hispanic,	CPRS, baseline interview
Time since		In years: index event – date at baseline	
Amputation		transhumeral, shoulder, interscalulothoracic	

Prosthesis type	Myoelectric, hybrid, cosmetic		
Bra size	Size of She-fit® bra ordered		
	nd Prosthetics User's Survey, UE=upper extremity, QL=qualitativ red Patient Record System	ve,	

- 6.6 No biological specimens will be collected.

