14.0 Withdrawal of Subjects

- 14.1 A subject may be withdrawn or preferably partially withdrawn from the research without their consent if they develop a condition on their residual body part that disallows them to wear a prosthesis, such as a bone spur or open sore.
- 14.2 The decision to withdraw will be made between the patient and the study physician.
- 14.3 Partial withdrawal is an option where the subject will discontinue wearing Brasthesis but will continue with the interview and focus group participation.

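### Protocol 10.4 ends participation for a residual-limb condition where 14.1 prefers partial withdrawal, and 14.3 does not secure that woman's primary post scores

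*Protocol*

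**What the plan says.** Two current protocol sections deal with a residual-limb condition that makes prosthesis wear impossible, and both give a bone spur and an open sore as examples.

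- **10.4** (Inclusion and Exclusion Criteria): "A subject will be ineligible to continue participation if they develop a condition on their residual body part" of this kind. No partial option is mentioned.
- **14.1** (Withdrawal of Subjects): she "may be withdrawn or preferably partially withdrawn from the research without their consent".
- **14.2**: the patient and the study physician make the withdrawal decision.
- **14.3**: under partial withdrawal she "will discontinue wearing Brasthesis but will continue with the interview and focus group participation".

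On outcomes, 4.1 says: "Primary endpoints are satisfaction, function, and comfort". Section 6.2 says: "The outcome measures administered at baseline will be completed again post-intervention". Those measures are the two OPUS sub-surveys and the one-item socket comfort rating. Table 1 in 6.5 gives the later timepoint as "Brasthesis - post".

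Section 6.4 covers a different case, the woman who goes back to her traditional harness. She stays in the study because "data on why participants use or do not use Brasthesis are needed to address research questions". Section 17.3 says that missing data can be collected but sets no rule. The SAP summarises pre-to-post change descriptively and does not mention participants who stop early.

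**The concern.** Staff cannot follow 10.4 and 14.1 together: one is mandatory and total, the other discretionary with a preference for retention. 14.2 settles who decides, not which rule governs.

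The primary post scores are at stake. The SAP's planned summary is change from baseline, so a woman without a post score contributes nothing to any primary table. The protocol's own reason in 6.4 for keeping non-users applies equally to a woman who stops because of her limb, yet 10.4 goes the other way. In a five-woman case series the individual results are the product, so a woman missing from the primary tables matters even though no hypothesis is tested.

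**Working it through.** The plan states no power, precision or event-rate figure, so there is nothing to reproduce. The check is a comparison of texts followed by simple shares.

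**Step 1: same trigger, different rule.** Sections 10.4 and 14.1 describe the same event with the same examples. Both are current text. The conflict is real.

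**Step 2: does the interview kept by 14.3 cover the surveys?** Three places suggest that it does not plainly do so:

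- 6.2 lists survey and brief interview as two sources of outcome data.
- 6.2 describes the repeat of the baseline measures and the post interview in separate sentences.
- Table 1 assigns the post interview to barriers (RQ 1.5). Satisfaction, function and comfort (RQ 1.2 to 1.4) have their own instruments.

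So 14.3 neither excludes nor secures the surveys.

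**Step 3: is there a fallback?** 6.2 places the repeat measures after the intervention, without saying when that falls for a woman who stops early. 17.3 gives no rule. Table 1 does not say which harness is rated by a woman who is wearing neither.

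**Step 4: scores per affected woman** (condition arising after fitting and before the post assessment):

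| Path | Primary post scores required |
|---|---|
| 10.4 followed literally | 0 of 3 |
| 14.3 as worded | 0 of 3 named, none excluded |
| 14.3 with the instruments named | 3 of 3, unless she is fully withdrawn |

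**Step 5: share of each primary table.** Five women are needed (12.2). One unreplaced loss leaves 5 − 1 = 4 pairs, and 1/5 = 20% of the pairs are missing on each of the three endpoints.

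**Step 6: what one missing value leaves open.** The Socket Comfort Score runs from 0 to 10. If a five-woman mean were reported, one unknown post value would leave it undetermined over a width of (10 − 0)/5 = 2 points. This is a bound on what is unknown, not an estimate of bias.

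**The case against.** The strongest reply is that 10.4 should not be read alone. It sits among the eligibility criteria, whereas Section 14 is the operative withdrawal section, and there retention is the stated preference. 6.2 repeats the measures without listing exceptions, at the same post-intervention step as the interview that 14.3 keeps. The retained interview covers barriers and the comparison with the traditional prosthesis, and the weekly contacts record problems. On the preferred path her experience is therefore not hidden.

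Much of this stands, and it lowers the weight of the point. It does not remove it: 10.4 is still a stated rule that a site could apply, and neither the interview nor the weekly contacts supply the three primary scores.

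A reader might also infer more than the documents support:

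- *That 14.3 drops the surveys.* It does not exclude them; it only fails to name them.
- *That the missing result would be poor.* The background section says that socket compression can damage tissue, so a sore may be related to fit. But a bone spur need not be, Brasthesis replaces the harness and not the socket, and the SAP expects little change at the socket interface. No direction can be claimed.
- *That up to half of the recruits could vanish behind complete tables,* from five needed and up to ten recruited. That ceiling would cover loss for any cause. It also assumes that dropouts are replaced and only completers tabled, and the documents state neither.

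**Conclusion.** The concern holds in limited form. Sections 10.4 and 14.1 conflict for the same event. Following 10.4 literally loses that woman's post satisfaction, function and comfort scores, and 14.3 as worded does not secure them.

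The size is 3 of 3 primary post scores for each affected woman, or 20% of each primary table for one woman among five. This assumes that the condition arises before the post assessment and that she is not replaced. If it arises before fitting is complete, there may be no Brasthesis experience to score. The documents give no rate for such conditions, so no frequency is claimed.

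Severity is minor to moderate: the event is contingent, the study is a descriptive pilot, and the effect is on the completeness of the primary description, not on any test.

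**What to change.** **Protocol 10.4.** Replace the ineligibility clause with: *will stop wearing Brasthesis and be handled under Section 14 (partial withdrawal preferred).*

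**Protocol 14.1 and 14.2.** Leave as they are, so that full withdrawal, decided with the study physician, remains available.

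**Protocol 14.3.** Add: *A fitted participant who stops Brasthesis, or is still not wearing it at week 4, completes both OPUS scales and the Socket Comfort Score by phone at stopping, or at week 4 at the latest, rating Brasthesis as last worn. The stop date and the harness rated are recorded.* The week-4 limit also covers a woman whose pause for a sore has not yet been judged permanent.

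**SAP, Aim 1.** Add: *Tables give the numbers enrolled, fitted, stopping early (with reason) and with post scores; early-stop scores are marked.*

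**Cost.** Edits to two protocol subsections, one SAP sentence, one data-sheet line and one phone call per early stopper. The baseline OPUS and comfort scores are already taken by phone, so no visit is added. She still stops wearing the harness, so her protection is unchanged.

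**Downside.** These scores reflect less than four weeks of wear and some recall, possibly several weeks if a pause runs on to week 4. That is why they are marked.

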11.0 Vulnerable Populations

11.1 No vulnerable populations will be included.

12.0 Local Number of Subjects

- 12.1 We will recruit up to 10 subjects.
- 12.2 Five subjects are needed to complete the research.

13.0 Recruitment Methods

13.1 We are proposing three recruitment paths to be initiated at the beginning of the project. The first path is to recruit through our current prosthetic patients and those of our prosthetic research colleagues in VISNs 2 and 20. Second, the Director of our Regional Amputation Center, PI [name], will present the study at a regularly scheduled National Amputation System of Care meeting. The Amputation System of Care network will provide a point of contact at each site to receive an email from the study project manager with a pertinent study description and contact information for women Veterans interested in the study. An IRB-approved study flyer with study contact information will be distributed electronically to all recruitment sites and will be included in the approach letters. The third path is to send approach letters to women Veterans with upper limb loss, identified in the VA Amputation Cube, following VA HIPAA policy. Patients will be identified by sex, upper limb unilateral limb loss, and elbow and above disarticulation/amputation. A list will be generated of the patients meeting these criteria.

If we cannot identify and consent five female Veteran amputees, we will recruit non-Veteran female amputees by dispersing IRB approved flyer to prosthetist colleagues. We will distribute IRB approved flyers at a national amputee conference. Non-Veterans may be required for this study because female upper extremity amputees are a small portion of the general population. Therefore, we may require non-Veterans to meet our enrollment goal. Veterans will be given preference. Non-Veterans will be used if we are unable to meet enrollment goals.

13.2

□ Email	☐ Online/Social Media Advertisement
⊠ Flyer	⊠ Record Review
⊠ Letter	☐ Other
□ News Advertisement	

- Flyer and approach letters uploaded.
- 13.3 N/A. Special and vulnerable populations not recruited.

14.0 Withdrawal of Subjects

- 14.1 A subject may be withdrawn or preferably partially withdrawn from the research without their consent if they develop a condition on their residual body part that disallows them to wear a prosthesis, such as a bone spur or open sore.
- 14.2 The decision to withdraw will be made between the patient and the study physician.
- 14.3 Partial withdrawal is an option where the subject will discontinue wearing Brasthesis but will continue with the interview and focus group participation.

15.0 Risks to Subjects

15.1 Based on our preliminary prototypes, the intervention should be more comfortable than standard care. To date, no physical risks associated with wearing a prosthetic harness have been published.

Many upper limb amputees have rejected their prostheses due to discomfort or difficulty using the prosthesis. Women amputees who have abandon their previous are eligible to enroll in this research. There is a risk that they will experience the discomfort and learning challenges again.

All research has inherent risks to privacy and/or confidentiality.

- 15.2 There are no risks to an embryo or fetus should the subject be or become pregnant.
- 15.3 There are no risks to others who are not subjects.

16.0 Potential Benefits to Subjects or Others

- 16.1 Individual subjects may experience increased comfort and function when using the Brasthesis harness as compared to the traditional harness, which in turn can increase function.
- 16.2 The study has the potential to offer women with an amputation a more comfortable, less expensive prosthetic harness option.

17.0 Data Management and Confidentiality

- 17.1 Because there will be only five subjects, descriptive analyses will be used.
- 17.2 All data will be stored electronically on the backed-up and protected JAHVH S-drive/Research/R drive Research/PROJECTS CURRENT/[name] Team/Brasthesis. There will be no paper data. All staff will be current on their privacy training. Identifiable data will be stored separately from informed consent documents and the crosswalk file. Only authorized team members (PI, project manager) will have access to protected data and documents. All data will remain at the JAHVH in the research protected environment for analysis. Access will be terminated for personnel who are no longer part of the research team. The project manager and PI will monitor compliance and to ensure that the HIPAA, IRB, and VA rules and regulations are being followed and met. The PI will be responsible for all incident reporting to the IRB and R&D Committee, ISSO and Privacy officer as appropriate.

17.3 Procedures that will be used to ensure the accuracy and quality of collected data include:

- Discussion of data at twice monthly research team meetings
- A single person collecting and entering data
- Opportunities exist to collect missing data

17.4 Handling data study-wide:

- See Table 1 in 6.5 for data collected. Identifiable information includes names, date of birth, telephone number, email address, medical record number (lastname+last 4 of SSN), and voice recording.
- Data will be stored per current VA policy RCS-10.
- Data will be destroyed per VA policy RCS-10.
- Confidential data will not be shared with anyone outside of the research group.

17.5

□Obtaining Signed Authorization	⊠Waiver of HIPAA Authorization for Recruitment/Screening Purposes Only
□Obtaining Online or Verbal Authorization (Alteration of HIPAA Authorization)	□Data Use Agreement
□Waiver of HIPAA Authorization for Entire Study	□Business Associate Agreement

- No PHI will be disclosed or received from individuals outside of the research group.
- For our requested waiver:
 - o Data will be acquired from the VHA Proclarity Analytics Server Amputation Cube (for the approach letters for recruiting purposes).
 - o Inclusion criteria: VISN, Facility, FY, Upper Limb, Female, Amputation level
 - o FY 2012 FY 2022
 - Only the PI and the project manager will have access to identifiers which will be located in a password protected file in the research project folder on the protected JAHVH research S-drive.
 - o For potential subjects who enroll, their name will be added to the crosswalk file that will be stored with the informed consent documents and separate from data. Data for potential subjects who decline to enroll will be destroyed immediately per VA policy. Data for potential subjects who cannot be contacted will be destroyed at six months into the study per VA policy, providing a 6-month response period.

- PHI will not be reused/disclosed to any other person or entity except as required by law, for authorized oversight of the research project, or for other research which use/disclosure of PHI would be permitted by the HIPAA privacy regulations.
- O It is not practicable to obtain signed HIPAA Authorizations from the subjects before using their PHI because we are going back 10 years in the records. We anticipate that we will not have current contact information for many of the potential subjects. It is not practicable as not all subjects will be eligible. Signed authorization will be obtained from subjects who are eligible and agree to participate.
- The study cannot be conducted without access to and use of subjects' PHI
 because we may not have a large enough sample size to successfully
 complete the study. We need access to PHI to verify eligibility.

